6.5. Concomitant Therapy

Any medications taken and changes in medications from the time the participant signing the study specific informed consent, up to final study contact Day +155 (± 14 days) will be recorded in the source data. Any medication (including over-the-counter or prescription medicines, vitamins, and/or herbal supplements) or other specific categories of interest) that the participant is receiving at the time of enrolment or receives during the quarantine/outpatient stage will be stored, prescribed and administered in line with their label-specific requirements, and recorded according to the parameters required by the clinical database.:.

Participants will be reminded to refrain from using any over-the-counter medication without the approval of the Investigator and must notify the site as soon as possible if they are prescribed any medication. All medications must be stopped prior to the planned date of dosing with IMP/viral challenge (whichever occurs first) unless in the opinion of the Investigator and/or Sponsor's Medical Monitor (SMM), the medication will not interfere with the study procedures or compromise participant safety. Medications prohibited throughout the study are shown in Table 2.

Table 2 Prohibited Medication

Prohibited medication	Washout
Systemic (oral and parenteral) antiviral drugs.	4 weeks prior to first study visit.
Use or anticipated use during conduct of the study of concomitant medications (prescription and non-prescription), including vitamins or herbal and dietary supplements within the specified windows, unless in the opinion of the Investigator the medication will not interfere with the study procedures or compromise participant safety.	7 days prior to the planned date of viral challenge: •Herbal supplements •Any medication or product (prescription or over the counter) for symptoms of nasal congestion •Short and long-acting antihistamines. Within 21 days prior to the planned date of viral challenge:

Prohibited medication	Washout
	
 •Chronically used medications, vitamins or dietary supplements, including any medication known to be moderate/potent inducers or inhibitors of CYP450 enzyme.
Any investigational medicinal product used in another trial	Within 3 months (or 5 half-lives of the investigational product used in the other trial), whichever is greater, prior to the planned date of viral challenge or dosing with IMP (whichever occurs first).

Any concomitant medication required for the participant's welfare may be given by the Investigator. However, it is the responsibility of the Investigator to ensure that details regarding the medication and the reason for its use are recorded appropriately in the source notes to permit their transfer to the clinical database.

The use of paracetamol and/or other allowed medications is permissible up to 7 days before the date of first dosing with IMP/viral challenge (whichever occurs first). During the study periods, the Investigator may permit a limited amount of paracetamol (no more than 4 g per day i.e. maximum daily dose) or topical medication, as clinically required for the treatment of headache or any other pain. Other medication to treat AEs may be prescribed if required.

Medications which are permitted throughout the study are shown in Table 3 below:

Table 3 Permitted Medication

Permitted medication	Time period
Paracetamol	Maximum 4g daily throughout the study duration at PI discretion.
Oral contraceptives	Allowed at any time during the study.
If, e.g. in an outbreak or pandemic, a newly instated national vaccine program is applicable to an individual participant, the PI and sponsor will discuss on an individual basis if concomitant vaccination may be allowed, study vaccine/inoculation postponed or the participant withdrawn from the study.	
Prescription and non-prescription medications, including vitamins or herbal and dietary supplements, not listed in prohibited medications are subject to approval by the PI.	

7. Discontinuation of Study Intervention/Withdrawal

7.1. Participant Withdrawal

A participant may withdraw their consent to participate in the study at any time, for any reason, without prejudice to his/her future medical care. Participants may decline to give a reason for their withdrawal. Additionally, the PI may withdraw a participant if, in their clinical judgement, it is in the best interest of the participant or if the participant cannot comply with the protocol. Wherever possible, the tests and evaluations listed for the Early Withdrawal Visit should be carried out, and if clinically indicated, the participant should be invited back for a final follow up visit.

The Sponsor should be notified of all study withdrawals in a timely manner, and in cases where the withdrawal is due to a medical reason the participant would be referred to his/her GP.

Participants will be counselled that early withdrawal from the viral challenge phase of the study is strongly discouraged, as it may pose a risk both to the participant and his/her contacts. In the event of a participant insisting on early withdrawal during the challenge isolation period, the participant will be encouraged to stay and would be advised of the potential risks of carrying RSV infection into the community, and to vulnerable groups in particular, as described in [Section 2.3.1](#).

If the participant withdraws consent for disclosure of future information, the Sponsor may retain and continue to use any data collected before such a withdrawal of consent.

If a participant withdraws from the study, he/she may request destruction of any samples taken and not tested, and the Investigator must document this in the site study records.

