
 To evaluate the safety and reactogenicity of RSVpreF, when compared to placebo 	
To evaluate the incidence of the following endpoints:
 
 Occurrence of solicited local reactions and systemic events within 7 days (i.e., on the day of vaccination and 6 subsequent days) after vaccination. Occurrence of unsolicited adverse events (AEs) within 30 days (i.e., on the day of vaccination and 29 subsequent days) after vaccination Occurrence of medically attended AEs (MAEs) and serious adverse events (SAEs) from vaccination (Day -28) up to study end (Day +155).

 To evaluate the safety of the RSV challenge model. 	
To list the incidence of the following endpoints:
 
 Occurrence of unsolicited AEs within 30 days post-viral challenge (Day 0) up to Day +28 follow up. Occurrence of SAEs related to the viral challenge from the viral challenge (Day 0) up to Day +28 follow up. Occurrence of haematological and biochemical laboratory abnormalities during the quarantine period. Use of concomitant medications within 30 days post-viral challenge (Day 0 up to Day +28 follow up).
TERTIARY	
Tertiary/exploratory endpoints include but are not limited to the following.	

 To evaluate the effect of baseline immune status on immunogenicity and efficacy of the RSVpreF, when compared to placebo 	
 The primary, secondary, and tertiary endpoints may be explored in relation to the baseline status of participants and the response to vaccination.

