7.2. Participant Discontinuation

Participants will be withdrawn from study intervention for the reasons listed below. These participants must not receive any additional intervention but should continue to be followed for safety. Additional unscheduled visits may be performed for safety reasons.

- Non-compliance with the study requirements and restrictions.
- Clinically significant abnormal laboratory findings, which in the opinion of the Investigator(s) and/or Sponsor, precludes further participation in the study.
- Development of inter-current illness which, in the opinion of the Investigator would compromise the health of the participant or the study objectives.
- The Investigator's decision that withdrawal from further participation would be in the participant's best interest.
- Termination of the study at the discretion of the Investigator(s) or Sponsor for safety, behavioural, or administrative reasons.
- The wish of the participant.
- Any intervention related SAEs.
- Anaphylactic reaction following dosing.
- The participant becomes pregnant.

When the target evaluable participant number is achieved, for a given quarantine group or for the overall study, reserve vaccinated participants may not be inoculated with challenge virus. In addition to post vaccination visits (1 and 7 days post vaccination), participants may additionally have assessments performed on Day -2/-1/0 and the final follow up visit Day +155 (± 14 days) for safety and immunogenicity.

Participants who are withdrawn from the study, will be requested to attend an Early Withdrawal Visit, with assessments as detailed in the SoA.

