4	
A severe non-serious adverse reaction (i.e. severe non-serious adverse events considered at least possibly related to the IMP administration) is reported in two participants, independent of whether or not within the same system-organ/class.
	
If such a status occurs at any point during the study, then further administration of RSVpref will not take place. The PI and the SMM will review the data and make decisions on whether it is appropriate to recommence dosing (via a substantial amendment, if indicated) or terminate the study.
 
Regulatory authority approval via a substantial amendment would be required in order to recommence the study.

In any event, participant follow-up should continue until resolution or stabilisation of AEs and final follow-up on Day +155 (\pm 14 days).

8. Study Assessments and Procedures

Unless otherwise stated, study assessments will be performed according to hVIVO SOPs.

Study procedures and their timing are summarised in the SoA. Protocol waivers or exemptions are not allowed. Adherence to the study design requirements, including those specified in the SoA, is essential and required for study conduct. Immediate safety concerns should be discussed with the Sponsor upon occurrence or awareness to determine if the participant should continue or discontinue study intervention

All screening evaluations must be completed and reviewed to confirm that potential participants meet all eligibility criteria. The investigator will maintain a screening log to record details of all participants screened and to document eligibility or record the reasons for screening failure, as applicable.

For all study assessments, the value obtained nearest to dosing will be used as the baseline measure for assessments, unless stated otherwise.

Procedures conducted as part of the hVIVO Generic Screening process and obtained before signing of the study specific Informed Consent Form (ICF) may be utilised for screening or baseline purposes provided the procedures met the protocol-specified criteria and were performed within the time frame defined in the SoA.

Where applicable, unless otherwise stated, normal ranges will be identified in the Investigator Trial Master File (TMF).

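### Sections 7.1, 7.2 and 7.5 leave follow-up unreconciled for overlapping withdrawal reasons, so late MAE/SAE ascertainment after investigator-initiated withdrawal can depend on perceived health

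*Combined protocol and SAP*

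**What the plan says.** Section 7.1 covers withdrawal from the study. Besides withdrawal of consent, it allows the investigator to withdraw someone when, in clinical judgement, "it is in the best interest of the participant or if the participant cannot comply with the protocol". On follow-up it says: "Wherever possible, the tests and evaluations listed for the Early Withdrawal Visit should be carried out". It then adds that, "if clinically indicated, the participant should be invited back for a final follow up visit".

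Section 7.2 covers withdrawal from study intervention. Its list of reasons includes "Non-compliance with the study requirements and restrictions" and an investigator's decision made in the participant's best interest. Its follow-up rule is unconditional: "These participants must not receive any additional intervention but should continue to be followed for safety". It names no visits and no end date. Its closing sentence requests an Early Withdrawal Visit from anyone withdrawn from the study, which agrees with 7.1.

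Section 7.5 adds, after the stopping-rules table: "In any event, participant follow-up should continue until resolution or stabilisation of AEs and final follow-up on Day +155".

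The endpoint that depends on this is in Section 3: MAEs and SAEs from vaccination (Day -28) to Day +155, a secondary safety endpoint. Section 9.3 places every vaccinated participant in the Safety Analysis Set, challenged or not.

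**The concern.** Two reasons, best interest and non-compliance, appear in both 7.1 and 7.2, and the follow-up attached to them differs. The distinction between leaving the study and stopping the intervention does not settle which section applies. Vaccination is a single dose, so before challenge, stopping the intervention means only that challenge is withheld. The best-interest item in 7.2 is itself worded as ending participation.

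If a site applies 7.1, the final contact depends on a judgement about the participant's health. That judgement is related to the outcome being counted, although it is not the same thing. Events after the Early Withdrawal Visit are then sought in people who seem unwell and not in the rest, while all of them remain in the safety population. If the number withdrawn differs by arm, the comparison of late MAE/SAE rates is affected as well.

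**Working it through.** No sample size, power or rate stated in the plan depends on this point, so there is no planned figure to reproduce. The check sets the texts side by side and then illustrates the possible size.

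**Texts**

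| | 7.1 | 7.2 | 7.5 |
|---|---|---|---|
| Status | Withdrawn from the study | Withdrawn from intervention | Not specified; placed under the stopping rules |
| Best interest, non-compliance | Both listed | Both listed | Not applicable |
| Visit at withdrawal | Early Withdrawal Visit where possible | Early Withdrawal Visit if withdrawn from the study | Not stated |
| Later follow-up | Final visit on clinical indication | Safety follow-up, no condition, no end date | To Day +155 |

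**What is collected after withdrawal under 7.1**

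- Section 8.17.2.3 finds MAEs through self-report, questions at visits and any telephone outreach the protocol specifies. The Schedule of Activities shows no such call for withdrawn participants.
- Section 8.17.1 does not oblige investigators to look for events once participation has ended.
- Section 8.17.3 follows events already reported. It does not find new ones.

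The nominal window is 28 + 155 = 183 days. Someone withdrawn at Day -2 has 2 + 155 = 157 days left, and 157/183 = 86%. The Early Withdrawal Visit covers only the time before it.

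**Illustration**

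Taken from the plan: up to 72 vaccinated (Section 9.2), so n = 36 per arm. The following are assumptions:

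- w = 2 or 5 withdrawn per arm. The plan's margin is 72 - 62 = 10, or 5 per arm, for all causes of not being challenged, so w = 5 is deliberately high.
- q = 5%, 10% or 20% later event risk.
- Of the withdrawn, only those with an event return, with probability r.

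Events seen: E = (n - w)q + wqr.

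Rate A, all vaccinated in the denominator: E/n.

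Rate B, only those with a final contact in the denominator: E/[(n - w) + wqr].

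Example for w = 5, q = 20%. With r = 1, E = 6.2 + 1.0 = 7.2 and rate B = 7.2/32 = 22.5%. With r = 0.5, E = 6.2 + 0.5 = 6.7 and rate A = 6.7/36 = 18.6%.

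| q | w | Rate B, r = 1 | Rate A, r = 0.5 |
|---|---|---|---|
| 5% | 2 | 5.28% | 4.86% |
| 5% | 5 | 5.76% | 4.65% |
| 10% | 2 | 10.53% | 9.72% |
| 10% | 5 | 11.43% | 9.31% |
| 20% | 2 | 20.93% | 19.44% |
| 20% | 5 | 22.50% | 18.61% |

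The error runs from 5.00 - 4.86 = 0.14 points to 22.50 - 20.00 = 2.50 points. The largest is 0.025 × 36 = 0.9 participants.

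Two cases show no bias. Rate A is correct when r = 1, because every event is found. Rate B is correct when return does not depend on the event.

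For an imbalance with no true difference, take q = 20%, five withdrawn in one arm and two in the other. Rate B differs by 22.50 - 20.93 = 1.6 points, and rate A by 19.44 - 18.61 = 0.8 points.

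**The case against.** The strongest reply is that the sections describe two different statuses and agree on the Early Withdrawal Visit, so the difference comes down to later contact. That is correct. A reader might infer that the sections prescribe opposite follow-up, and the documents do not support that. What stands is that the follow-up differs for shared reasons and that nothing assigns a case to one section.

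A reader might also infer that the 6-month safety data as a whole depend on the outcome. They do not. Only participants withdrawn from the study are affected, and only for events after withdrawal. Intervention-related SAEs, anaphylaxis and laboratory findings that preclude participation are named in 7.2 alone, where safety follow-up is unconditional. Section 10.3.10 requires reporting of SAEs up to the last participant's last scheduled visit, which covers part of the serious events. Section 6.3 keeps the investigator blinded, which limits deliberate differences between arms. The remaining gap is mainly new, non-serious MAEs.

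Nor do the documents say that an unobserved participant counts as event-free. Section 9.6.8 reports numbers and percentages of participants, but Section 9.5 defers missing data to the detailed SAP, which is not in the document reviewed. That SAP could settle the denominator, but it could not recover events that nobody asked about.

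Finally, the effect is small beside chance. At 20% of 36 the binomial SD is √(36 × 0.2 × 0.8) = 2.4 participants, and safety is summarised descriptively in an exploratory study. This argues for a modest rating. It does not justify leaving the texts unreconciled.

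**Conclusion.** The inconsistency is real and limited. Sections 7.1, 7.2 and 7.5 need reconciling. As written, 7.1 makes active ascertainment of late events conditional on clinical status for participants whom the investigator withdraws from the study.

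The direction of any bias depends on the denominator: upward among those with a final contact, downward among all vaccinated if some events are missed. The illustrated size is about 0.1 to 2.5 percentage points, under one participant per arm. It rests on assumed withdrawal numbers, event risks and return probabilities, because the documents give none of these. If no withdrawn participant returned at all, the w = 5, q = 20% case would miss 5 × 0.20 = 1.0 event (1/36 = 2.8 points), but that is plain loss of follow-up, not selective return.

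The 10-person margin cannot serve as a forecast. It also covers withdrawn consent, reserves not challenged and participants found ineligible at quarantine entry.

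**What to change.** Reconcile 7.1, 7.2 and 7.5. State which section applies when the investigator initiates withdrawal, and whether the Day +155 sentence in 7.5 is general or confined to the stopping rules. The investigator's authority to withdraw a participant stays as it is.

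For data collection, replace the clinical-indication condition in 7.1 with an MAE/SAE query at Day +155, by visit or telephone, for every vaccinated participant who has not withdrawn consent to further contact. Add that contact to the Schedule of Activities.

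The cost is a wording change and a few telephone calls. Sections 8.17.2.3 and 10.3.6.1 already foresee contact by telephone. Participants who refuse further contact will still be missing, and the detailed SAP should state the denominator used for them.

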7.2. Participant Discontinuation

Participants will be withdrawn from study intervention for the reasons listed below. These participants must not receive any additional intervention but should continue to be followed for safety. Additional unscheduled visits may be performed for safety reasons.

- Non-compliance with the study requirements and restrictions.
- Clinically significant abnormal laboratory findings, which in the opinion of the Investigator(s) and/or Sponsor, precludes further participation in the study.
- Development of inter-current illness which, in the opinion of the Investigator would compromise the health of the participant or the study objectives.
- The Investigator's decision that withdrawal from further participation would be in the participant's best interest.
- Termination of the study at the discretion of the Investigator(s) or Sponsor for safety, behavioural, or administrative reasons.
- The wish of the participant.
- Any intervention related SAEs.
- Anaphylactic reaction following dosing.
- The participant becomes pregnant.

When the target evaluable participant number is achieved, for a given quarantine group or for the overall study, reserve vaccinated participants may not be inoculated with challenge virus. In addition to post vaccination visits (1 and 7 days post vaccination), participants may additionally have assessments performed on Day -2/-1/0 and the final follow up visit Day +155 (± 14 days) for safety and immunogenicity.

Participants who are withdrawn from the study, will be requested to attend an Early Withdrawal Visit, with assessments as detailed in the SoA.

7.2.1. Temporary Discontinuation / Temporary Delay in Enrolment

At the first study visit if a participant is found to be ineligible due to transient circumstances (such as acute disease and/or fever), dosing will be postponed until the transient circumstances have been resolved and the participant will be re-invited to a later quarantine group within the allowed time window. For participant rescreening refer to [Section 5.4](#).

7.3. Lost to Follow up

A participant will be considered lost to follow-up if he or she repeatedly fails to return for scheduled visits and is unable to be contacted by the study site.

The following actions must be taken if a participant fails to return to the clinic for a required study visit:

- The site must attempt to contact the participant and reschedule the missed visit as soon as possible and counsel the participant on the importance of maintaining the assigned visit schedule and ascertain whether or not the participant wishes to and/or should continue in the study.
- Before a participant is deemed lost to follow up, the Investigator or designee must make every effort to regain contact with the participant (where possible, 3 telephone calls and, if necessary, a follow-up letter to the participant's last known mailing address or local equivalent methods). These contact attempts should be documented in the participant's medical record.
- Should the participant continue to be unreachable, he/she will be considered to have withdrawn from the study.

7.4. Participant Replacement Strategy

Participants who have been vaccinated but not inoculated may be replaced in order to achieve the planned evaluable number of participants if deemed appropriate by the PI and with the approval of the Sponsor.

The replacement participant will be assigned to the same group as the original (discontinued) participant. The replacement participant will be assigned a new, unique randomisation number equaling the randomisation number of the replaced participant, plus 100; for example, participant 001 would be replaced by participant 101). This will ensure that the replacement participant receives the same allocated blinded treatment as the participant who is being replaced.

7.5. Stopping Rules

The PI and the SMM will perform safety reviews on available clinical and virology data as appropriate during the quarantine period.

Four clinical scenarios relating to the incidence of SAEs/SUSAR during the study and the procedures that should be performed in each case are presented in the Table 4 below:

Table 4 Study Stopping Rules

Status	Criterion	Procedure
1	No SUSAR have been reported but an overall pattern of clinical changes or symptoms exists, attributed to the IMP, which may appear minor or moderate in terms of individual AEs but which collectively represent a concern for safety.	
If such a status occurs at any point during the study, then further administration of IMP will not take place. The PI and the SMM will review the data and make a decision on whether it is appropriate to recommence dosing or terminate the study.
 
Regulatory authority approval via a substantial amendment would be required in order to recommence the study.

2	
Unexpected virus-related SAE or unexpected virus-related AEs of clinical concern have been reported following Human Viral Challenge.
 
*Expectedness will be assessed by referring to the challenge virus dossier
	
If such a status occurs at any point during the study then the PI and the SMM will review the data and make a decision based on expectedness* of the viral event.
 
If the event is unexpected, further administration of the virus will not take place. The PI and the SMM will review the data and make a decision on whether it is appropriate to recommence inoculation or terminate the study.
 
Regulatory authority approval via a substantial amendment would be required in order to recommence the study.

3	A serious adverse reaction (SAR) (i.e. a SAE considered at least possibly related to the IMP administration) has been reported in one participant.	
If such a status occurs at any point during the study, then further administration of RSVpreF will not take place. The PI and the SMM will review the data and make decisions on whether it is appropriate to recommence dosing or terminate the study.
 
Regulatory authority approval via a substantial amendment would be required in order to recommence the study.

Status	Criterion	Procedure
4	
A severe non-serious adverse reaction (i.e. severe non-serious adverse events considered at least possibly related to the IMP administration) is reported in two participants, independent of whether or not within the same system-organ/class.
	
If such a status occurs at any point during the study, then further administration of RSVpref will not take place. The PI and the SMM will review the data and make decisions on whether it is appropriate to recommence dosing (via a substantial amendment, if indicated) or terminate the study.
 
Regulatory authority approval via a substantial amendment would be required in order to recommence the study.

In any event, participant follow-up should continue until resolution or stabilisation of AEs and final follow-up on Day +155 (\pm 14 days).

8. Study Assessments and Procedures

Unless otherwise stated, study assessments will be performed according to hVIVO SOPs.

Study procedures and their timing are summarised in the SoA. Protocol waivers or exemptions are not allowed. Adherence to the study design requirements, including those specified in the SoA, is essential and required for study conduct. Immediate safety concerns should be discussed with the Sponsor upon occurrence or awareness to determine if the participant should continue or discontinue study intervention

All screening evaluations must be completed and reviewed to confirm that potential participants meet all eligibility criteria. The investigator will maintain a screening log to record details of all participants screened and to document eligibility or record the reasons for screening failure, as applicable.

For all study assessments, the value obtained nearest to dosing will be used as the baseline measure for assessments, unless stated otherwise.

Procedures conducted as part of the hVIVO Generic Screening process and obtained before signing of the study specific Informed Consent Form (ICF) may be utilised for screening or baseline purposes provided the procedures met the protocol-specified criteria and were performed within the time frame defined in the SoA.

Where applicable, unless otherwise stated, normal ranges will be identified in the Investigator Trial Master File (TMF).

